5.1.12.8 Discontinuation of DMF background therapy

Subjects who permanently discontinue DMF background therapy must permanently discontinue study treatment and may begin treatment with an approved MS therapy in accordance to local practices.

5.2 Previous and concomitant therapy

5.2.1 Definitions

A previous therapy is any treatment for which the end date is prior to the start of study (i.e., signing of informed consent).

A study-concomitant therapy is any therapy which is ongoing or initiated after signing of informed consent, and initiated before EOS visit. All study-concomitant therapies must be captured in the eCRF [see Section 5.2.2.1].

Study concomitant therapies include study treatment-concomitant therapies, which is any therapy either ongoing at the start of study treatment or initiated during the study treatment period, or up to 30 days after the end of study treatment.

5.2.2 Reporting of previous/concomitant therapy in the eCRF

5.2.2.1 *Study-concomitant therapies*

The use of all study-concomitant therapy (including traditional and alternative medicines, i.e., plant-, animal-, or mineral-based medicines; see definition in Section 5.2.1) will be recorded in the Concomitant Medications form of the eCRF. Contraceptives will be recorded in a specific Contraceptive Methods form of the eCRF. The generic name, start/end dates of administration (as well as whether it was ongoing at start of treatment and/or EOS), route, dose, frequency, and indication will be recorded in the corresponding forms of the eCRF. DMF intake (i.e., the background concomitant therapy) will be recorded on a specific log of the eCRF [see Section 5.2.2.3]).

5.2.2.2 *Previous MS therapies*

Any previous administration of disease-modifying treatment for MS (e.g., IFN β -1a [Rebif[®] - Avonex[®], Plegridy[®]], IFN β -1b [Betaferon[®], Extavia[®]], glatiramer acetate [Copaxone[®], Glatopa[®]], natalizumab [Tysabri[®]], teriflunomide [Aubagio[®]], mitoxantrone [Novantrone[®]], alemtuzumab [Lemtrada[®]], daclizumab [Zynbryta[®]], ocrelizumab [Ocrevus[®]], cladribine [Mavenclad[®]]), at any time prior to Visit 1 (Screening) will be recorded in the previous MS treatment form of the eCRF [see Section 1.1.4]. For treatments received in the last 24 months prior to the study, start date, end date and reason for discontinuation will be recorded in the eCRF. In addition, dose, route, and frequency should be recorded in the eCRF, if available. For treatments stopped before the last 24 months prior to the study, start date, end date, and reason for discontinuation may be reported only if known and evidenced in the source documents.

The therapies used for the treatment of relapses experienced by the subject in the past 24 months will be recorded in the previous MS treatment form of the eCRF (e.g., corticosteroids, ACTH). For each therapy, the start date, end date, reason for discontinuation, dose, route, and frequency of administration will be recorded in the eCRF.

5.2.2.3 *Other previous therapies*

Any previous relevant therapy as per principal investigator / treating neurologist judgment (e.g., therapies listed in exclusion criteria, therapies for relevant medical history) will be recorded in the Previous Medications form of the eCRF.

5.2.3 *Concomitant background therapy*

In order to be eligible for this study, subjects must have been treated with DMF (Tecfidera[®]) for at least 6 months prior to Visit 1 (Screening). Subjects should be treated with DMF as per prescribing information [[Tecfidera USPI](#), [Tecfidera SmPC](#)] throughout the course of the study [see Section [3.5.2.1](#)].

Any previous administration including, if applicable, the last initiation of DMF (Tecfidera[®]) prior to Visit 1 (Screening) as well as intake (start date, end date, dose change, and reason for interruption and/or discontinuation) during the study must be recorded in the DMF-specific log of the eCRF.

5.2.4 *Recommended concomitant therapy*

Treatment of relapses:

- If a relapse requires treatment with corticosteroids, methylprednisolone 1 g i.v., oral methylprednisolone in the dose range of 1 g to 1.25 g or equivalent doses of oral prednisone or prednisolone daily for 3 to 5 days is recommended (without an oral taper). These administrations will be reported in the eCRF. Treatment with other corticosteroids, another dose, other routes of administration, or ACTH is not recommended unless deemed necessary and must be documented in the patient charts by the investigator.
- Treatment of relapses with plasma exchange (i.e., plasmapheresis, cytapheresis) is prohibited. The effect of plasmapheresis on relapse recovery is not sufficiently well documented to justify its inclusion as part of the protocol. Allowing plasmapheresis as per investigator discretion would lead to inhomogeneous treatment of relapses which could affect the study outcome in an unpredictable direction.

5.2.5 *Allowed concomitant therapy*

- Dalfampridine (synonymous with fampridine) on a stable dose for at least 90 days prior to randomization and during double blind treatment. Dalfampridine therapy must not be started or increased in dose during the study. Stopping or decreasing the dose of dalfampridine during the study should only take place if deemed absolutely necessary by the investigator;
- Administration of i.v. atropine in the event of symptomatic bradycardia;

- Short-acting β 2-agonists for respiratory symptoms and/or reduced pulmonary function during study treatment (please refer to Sections 5.1.12.4 and 7.3.3 for guidance);
- QT-prolonging drugs with known risk of Torsades de Pointes should be used with caution since ponesimod may potentially enhance their effect on QT interval (guidance is provided in [Appendix 4](#));
- Vaccination with non-live vaccines. Subjects receiving non-live vaccination while on study treatment will have 5 mL of blood drawn prior to and \geq 3 weeks after vaccination in order to explore changes in vaccine-specific antibody titers from pre-to post-vaccination. Samples will be analyzed at the end of the study;
- Low dose of corticosteroids (up to 10 mg of prednisone equivalent daily), given as short-term treatment (up to 2 weeks per treatment cycle with at least 8 weeks' interval between treatment cycles and no more than 8 weeks during the whole study duration)
- Inhaled corticosteroids for pulmonary conditions;
- Other treatments considered necessary for the subject's benefit and not categorized as prohibited concomitant medications.

5.2.6 Forbidden concomitant therapy

The below list of forbidden concomitant therapies is applicable to all subjects receiving study treatment, but not to the subjects who prematurely discontinued study treatment and participate in the PTOP.

- Systemic corticosteroids and ACTH, except for: the treatment of MS relapses [see Section 5.2.4]; short-term treatment with a low dose of corticosteroid; and inhaled corticosteroids for pulmonary conditions [see Section 5.2.5];
- Disease-modifying drugs for MS other than prescribed as per protocol (e.g., IFN β , glatiramer acetate, fingolimod, teriflunomide, natalizumab or other monoclonal antibody therapy);
- Immunosuppressive treatment (e.g., cladribine, mitoxantrone or other systemic immunosuppressive treatments such as azathioprine, cyclophosphamide, cyclosporine, methotrexate, or leflunomide);
- Intravenous immunoglobulin;
- Plasmapheresis, cytapheresis, or total lymphoid irradiation;
- Vaccination with live vaccines;
- β -blockers, diltiazem, verapamil, digoxin, or any other anti-arrhythmic or HR lowering systemic therapy [non-exhaustive list of drugs provided in [Appendix 3](#)];
- Any other investigational drug;

- Any investigational therapeutic procedure for MS (e.g., stent placement or angioplasty for chronic cerebrospinal venous insufficiency (CCSVI), stem cell transplantation).

In the event that a subject takes any of these forbidden medications, the investigator must contact the sponsor to discuss further FU actions including stopping/interrupting study treatment as appropriate.

6 STUDY ENDPOINTS

6.1 Efficacy endpoints

For each of the study efficacy endpoints, baseline is defined as the last value recorded prior to randomization (the actual visit used as baseline might be different across endpoints).

6.1.1 Primary efficacy endpoint

The primary endpoint is ARR. This endpoint is defined as the number of confirmed relapses from randomization up to EOS, per subject-year.

Definition of relapse

- A relapse is defined as new, worsening or recurrent neurological symptoms that occur at least 30 days after the onset of a preceding relapse, and that last at least 24 hours, in the absence of fever or infection.
- The new, worsening or recurrent neurological symptoms are to be evaluated by the treating neurologist and, if all the elements of the above definition have been verified, in the absence of another, better explanation of the subject's symptoms, the event is considered as a relapse [see Section 7.2.2]. The onset date of the relapse corresponds to the onset date of the symptoms.
- A relapse will be confirmed only when the subjects' symptoms are accompanied by an increase in EDSS/FS scores, which is consistent with the subject's symptoms, from a previous clinically stable EDSS/FS assessment (i.e., performed at least 30 days after the onset of any previous relapse), obtained by the efficacy assessor and consistent with the following:
 - an increase of at least half a step (0.5 point; unless EDSS = 0, then an increase of at least 1.0 point is required), or
 - an increase of at least 1.0 point in at least two FS scores, or
 - an increase of at least 2.0 points in at least one FS score (excluding bladder/bowel and cerebral).

6.1.2 Secondary efficacy endpoints

There are five secondary efficacy endpoints, which will be analyzed in a hierarchical manner:

- Time to 12-week CDA from baseline up to EOS.

Definition: A 12-week CDA is:

- an increase of at least 1.5 in EDSS for subjects with a baseline EDSS score of 0, or
- an increase of at least 1.0 in EDSS for subjects with a baseline EDSS score of 1.0 to 5.0, or
- an increase of at least 0.5 in EDSS for subjects with a baseline EDSS score ≥ 5.5

which is to be confirmed after 12 weeks.

Baseline EDSS is defined as the last EDSS score recorded during pre-randomization. The initial EDSS increase, meeting the above criteria, is defined as the onset of disability accumulation. All EDSS measurements (with or without relapse, at a scheduled or unscheduled visit) will be used to determine the onset of disability accumulation. However, for the purpose of confirmation, only EDSS measured more than 30 days after the onset of a confirmed relapse will be used. This is to avoid a confirmation of disability accumulation caused by a relapse. In order to confirm that the EDSS increase is persistent, all EDSS measurements between the onset and the 12-week EDSS confirmation (minus visit time-window) need to show an increase in EDSS, meeting the criteria for accumulation of disability as defined above.

- Time to first confirmed relapse up to EOS.

Definition: Relapse definition is given in Section 6.1.1. Date of the first confirmed relapse is defined as the onset date of the first confirmed relapse.

- Mean number of combined unique active lesions (CUALs) per subject per post-baseline MRI scan up to EOS.

Definition: CUALs are new Gd+ T1 lesions plus new or enlarging T2 lesions (without double-counting of lesions).

- Longitudinal change over time in fatigue-related symptoms as measured by the symptoms domain of the FSIQ-RMS from baseline up to EOS.
- Longitudinal percent change over time in brain volume from baseline up to EOS.

Definition: Longitudinal brain volume measurements are derived from MRI scans by using Structural Image Evaluation, using Normalisation, of Atrophy methodology (SIENA) [Smith 2001, Smith 2002].

6.1.3 Other efficacy endpoints

MRI-based exploratory endpoints:

- Percent change in brain volume (PCBV) from baseline to Weeks 48, 96, 144, EOT, and EOS;
- Mean number of CUALs per subject per scan from baseline up to Weeks 48, 96, 144, EOT, and EOS;
- Mean number of Gd+T1 lesions per subject per scan from baseline up to Weeks 48, 96, 144, EOT, and EOS;
- Mean number of new or enlarging T2 lesions per subject per scan from baseline to Weeks 48, 96, 144, EOT and EOS;
- Change in the volume of MRI lesions (T2 lesions, T1 hypointense lesions) from baseline to Weeks 48, 96, 144, EOT, and EOS;
- Absence of MRI lesions (Gd+ T1 lesions, new or enlarging T2 lesions, new T1 hypointense lesions) from baseline to Weeks 48, 96, 144, EOT, and EOS.

Clinical exploratory endpoints (disease activity, relapses, disability progression):

- Absence of confirmed relapses from baseline up to EOS;
- Time to first 24-week CDA from baseline up to EOS;

Definition: A 24-week CDA is:

- an increase of at least 1.5 in EDSS for subjects with a baseline EDSS score of 0, or
- an increase of at least 1.0 in EDSS for subjects with a baseline EDSS score of 1.0 to 5.0, or
- an increase of at least 0.5 in EDSS for subjects with a baseline EDSS score ≥ 5.5 ,

which is to be confirmed after 24 weeks.

Baseline EDSS is defined as the last EDSS score recorded during pre-randomization. The initial EDSS increase, meeting the above criteria, is defined as the onset of disability accumulation. All EDSS measurements (with or without relapse, at a scheduled or unscheduled visit) will be used to determine the onset of disability accumulation.

However, for the purpose of confirmation, only EDSS measured more than 30 days after the onset of a confirmed relapse will be used. This is to avoid a confirmation of disability accumulation caused by a relapse. In order to confirm that the EDSS increase is persistent, all EDSS measurements between the onset and the 24-week EDSS confirmation (minus visit time-window) need to show an increase in EDSS, meeting the criteria for accumulation of disability as defined above.

- Change in EDSS from baseline by visit up to EOS;
- No evidence of disease activity (NEDA) status at EOS (defined by the absence of confirmed relapse, Gd+ T1 lesions, new or enlarging T2 lesions, 12-week CDA, as well as absence of annual brain volume decrease $\geq 0.4\%$ from baseline to EOS and completing treatment as planned).

Other clinical exploratory endpoints:

- Change in MSFC Z-score from baseline by visit up to EOS;
- Change in the SDMT score from baseline by visit up to EOS;
- Change from baseline by visit up to EOS in fatigue-related impacts as measured by the impact sub-scales of the FSIQ-RMS.

6.2 Safety endpoints

The treatment-emergent period is defined as the time from first study drug intake up to 30 days (inclusive) after last study drug intake. The following safety endpoints will be analyzed:

- Treatment-emergent AEs, SAEs, AEs of special interest[#], MACE, and AEs leading to premature discontinuation of study treatment;
- Treatment-emergent morphological ECG abnormalities (as defined by the ECG provider);
- Change in 12-lead ECG variables (HR, PR, QRS, QT, QT corrected for HR on the basis of Bazett's formula [QTcB], Fridericia's formula [QTcF]) from pre-dose to selected post-dose assessments (1 h, 2 h, 3 h, 4 h) on Day 1 and on day of re-initiation of study treatment when post-dose monitoring is required;
- Notable abnormalities* for selected 12-lead ECG variables (HR, PR, QT, QTc) at 3-hour post-dose assessment on Day 1, Week 12 and at the re-initiation of study treatment when post-dose monitoring is required;
- Treatment-emergent decrease of FEV₁ or FVC $> 20\%$ from baseline values or decrease of percent predicted FEV₁ or FVC > 20 percentage points from baseline values;
- Change in FEV₁ or FVC from baseline, absolute and % of absolute change to all timepoints up to EOS;

- Change from baseline to EOS versus change from baseline to EOT in FEV₁ or FVC (absolute and % of predicted);
- Among subjects with a decrease of > 200 mL or > 12% in FEV₁ or FVC from baseline to EOT, reversibility defined as a decrease of < 200 mL or < 12% in FEV₁ or FVC from baseline to last available post EOT follow-up;
- Treatment-emergent notable blood pressure abnormalities*;
- Treatment-emergent notable laboratory abnormalities*;
- Change in body weight from baseline to EOS;
- Treatment-emergent electronic self-rated version of the Columbia-Suicide Severity Rating Scale (eC-SSRS) suicidal ideation score of 4 or above, or a “yes” response on the eC-SSRS suicidal behavior item;
- Change in JCV serology from baseline up to EOS.

[#] The selection of AEs of special interest is based on the anticipated risks of treatment with ponesimod and on the events that may be related to MS co-morbidities (e.g., seizures or stroke) as described in [Appendix 5](#); the final list of AEs of special interest will be defined in the Statistical Analysis Plan (SAP).

* The selection of notable abnormalities considered for the analyses is based on standard definitions and the anticipated risks of treatment with ponesimod as described in [Appendix 6](#); the final list of abnormalities will be defined in the SAP.

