8.3.1.2 Visit 20 – FU

If a temporary interruption of study treatment lasts more than 30 days and leads to permanent premature discontinuation, Visit 20 (FU) can be combined with the EOT visit.

The FU visit will take place at least 30 days after the last dose of study treatment, but no later than 37 days after last dose of study treatment. The visit includes:

- EDSS/FS.
- MS Relapse.
- FSIQ-RMS. At Visit 20 (FU), the FSIQ-RMS will be completed at home prior to the visit, ideally, during the 7 consecutive days preceding the visit.
- Recording of changes in concomitant medications.
- Body temperature.
- SBP/DBP.
- 12-lead ECG.
- Ophthalmological examination.
- Spirometry.
- Urinalysis.
- Hematology (including lymphocytes*), blood chemistry.
- PK sampling.

- Lymphocyte subsets (only at sites participating in sub-study).
- Serum pregnancy test for WOCBP.
- Recording of AEs and SAEs.

* If a total lymphocyte count $< 0.5 \times 10^9/L$ is observed at FU, an alert will be sent to the principal investigator and the sponsor [see Section 7.3.13.1]. Discontinuation of DMF treatment should be considered in accordance with prescribing information [Tecfidera USPI, Tecfidera SmPC].

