11.3.5 Analysis of the safety variables

The SAF will be used to perform all safety analyses.

If not otherwise stated, only treatment-emergent safety data (observations up to 30 days after study drug discontinuation) will be considered in tables and figures. All safety data will be included in listings, with flags for safety data not considered to be treatment-emergent.

Specific safety events (AEs, laboratory tests, ECG findings, etc.) will be considered. In general, they consist of one or more well-defined safety events which are similar in nature and for which there is a specific clinical interest in connection with ponesimod.

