11.3.5.3 Pulmonary safety

Descriptive summary statistics by visit and study treatment will be provided for observed treatment-emergent values and changes from baseline by visit in FEV₁ and FVC (all expressed in absolute change, % change and % of predicted value).

The number and proportion of treatment-emergent decreases of percent predicted FEV₁ or FVC > 20% from baseline at any time up to EOT + 30 will be summarized by treatment.

The trend effect of treatment of the percent predicted FEV₁ over time will be analyzed by treatment using a regression analysis with time as the independent variable and % predicted FEV₁ calculated with the age at the time of the assessment as the dependent variable. Assessments during up-titration and after the subject discontinues treatment will not be included in this analysis.

The mean (and 95% CIs), change and % change from baseline to EOS and from baseline to EOT in FEV₁ or FVC (absolute and % of predicted) will be plotted by treatment. A scatter plot will display the change from baseline to EOS versus the change from baseline to EOT on an individual subject level by study treatment.

For the subset of subjects with a decrease of > 200 mL or > 12% in FEV₁ or FVC from baseline at EOT, the number and percentage of subjects with a decrease of ≤ 200 mL and ≤ 12% from baseline to last available FU in FEV₁ or FVC will be summarized by treatment.

Pulmonary safety events will be summarized as categorical variables.

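### Default safety tables stop at day 30 after the last dose, when the follow-up visit window (days 30–37) opens, so most follow-up laboratory, BP and ECG values taken later reach listings only

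*Protocol*

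**What the plan says.** Section 6.2 of the protocol defines the window: "The treatment-emergent period is defined as the time from first study drug intake up to 30 days (inclusive) after last study drug intake". Section 11.3.5 makes it the default for display: unless otherwise stated, "only treatment-emergent safety data (observations up to 30 days after study drug discontinuation) will be considered in tables and figures". Data outside the window are kept: "All safety data will be included in listings, with flags for safety data not considered to be treatment-emergent".

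Section 8.3.1.2 places the FU visit (Visit 20) "at least 30 days after the last dose of study treatment, but no later than 37 days after last dose of study treatment". Table 2 agrees, with a target of last intake + 30 days and a window of + 7 days. The visit includes hematology, chemistry, urinalysis, BP, 12-lead ECG and spirometry.

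The detailed analysis sections repeat the limit. The by-visit summaries in 11.3.5.2 (ECG), 11.3.5.3 (spirometry), 11.3.5.4 (BP) and 11.3.5.5.1 (laboratory) are of treatment-emergent values. Morphological ECG findings, notable BP abnormalities and laboratory safety events, including the liver criteria for ALT, AST and bilirubin in 11.3.5.5.2, are also treatment-emergent. The count of FEV₁/FVC decreases above 20% runs to EOT + 30, and section 11 defines the EOT date as the date of the last dose.

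Some outputs are not cut at day 30. Section 6.2 lists "Change in FEV₁ or FVC from baseline, absolute and % of absolute change to all timepoints up to EOS", and a reversibility endpoint measured "from baseline to last available post EOT follow-up". Section 11.3.5.3 adds that "change and % change from baseline to EOS and from baseline to EOT in FEV₁ or FVC (absolute and % of predicted) will be plotted by treatment". Section 11.3.5.5.1 plots lymphocyte change to EOS.

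**The concern.** The analysis window closes on the first day on which the FU visit may take place. Followed as written, a subject's FU liver tests, other chemistry, BP or ECG enter a table if the visit fell on day 30 and leave it if the visit fell on day 31. That split has no clinical meaning and depends only on scheduling.

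For subjects who complete treatment, FU is the EOS visit (section 3.5.3.3) and so their last scheduled off-drug check of ECG, BP and chemistry. Sections 1.4 and 1.5 name liver enzyme elevations, blood pressure and HR/AV conduction effects among ponesimod's potential risks, and the liver as a target organ shared with DMF. These are the measurements for which a reader of the study report would want recovery or late change tabulated by arm.

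**Working it through.** **1. Overlap of the windows.** With day 0 as the last dose:

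- Treatment-emergent data end at day 30 inclusive (6.2).
- Permitted FU days are 30, 31, …, 37 (8.3.1.2; Table 2): 37 − 30 + 1 = 8 days.
- Inside the treatment-emergent window: day 30 only, 1 of 8 = 12.5%.
- Outside it: days 31 to 37, 7 of 8 = 87.5%.

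The plan states no figure of its own to reproduce. The count leaves aside FU visits combined with EOT after a treatment interruption of more than 30 days (8.2.10, 8.3.1.2).

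**2. From days to visits.** The protocol gives no distribution of actual visit days. If every visit fell on day 30, all FU values would be tabulated. If every visit fell later, none would. An even spread over the 8 days would give 12.5% tabulated and 87.5% listed only, but that spread is an assumption, and the + 30 day target in Table 2 could equally lead to clustering on day 30. The share of visits lost could be anything from 0% to 100%.

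**3. Which outputs are touched by an FU value from days 31–37.**

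- *Laboratory other than lymphocytes:* out of the by-visit summary (11.3.5.5.1) and the laboratory safety events (11.3.5.5.2).
- *Lymphocytes:* out of the by-visit summary, but change to EOS is plotted.
- *BP:* out of the by-visit summary and the notable-abnormality summary (11.3.5.4).
- *ECG:* out of the by-visit summary and the morphological findings (11.3.5.2). The notable-abnormality endpoint uses only the 3-hour post-dose recordings on Day 1, at Week 12 and at re-initiation, so an FU ECG could never enter it.
- *Spirometry:* out of the by-visit summary and the above-20% decrease count. Still used in the EOS plots and scatter plot when FU is the EOS visit, and in the reversibility table when FU is the last available follow-up (11.3.5.3).

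**4. Is there another table for these values?** Section 11.3.5.1.4 summarises events more than 30 days after discontinuation, but only AEs and SAEs. No equivalent is given for non-lymphocyte laboratory tests, BP or ECG.

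**5. Effect of a window matched to the visit.** If FU measurements up to day 37 are assigned to their own column, 8 of 8 permitted days are covered instead of 1 of 8.

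**The case against.** The best defence is that the cut-off is deliberate. The half-life is about 32 hours (1.3.2.1), so day 30 is 720 / 32 = 22.5 half-lives after the last dose. Values from days 31–37 are essentially off drug, and the limit matches the AE definition in 10.1.1. This stands as a reason not to add those days to treatment-emergent abnormality counts. It does not explain why a day-30 FU value is tabulated and a day-31 value from the same scheduled visit is not.

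A second defence is that the SAP holds the full details and that the default rule allows exceptions. That is true, and the SAP may assign FU values to a visit. But the protocol itself states a cut-off that clashes with its own visit window, and its detailed sections and endpoint labels repeat it. This is a stated rule, not an omitted detail.

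Third, nothing is lost from the database. All values are listed with flags, clinically relevant laboratory findings are reported as AEs (7.3.13.1), and late AEs have their own summary. This limits the harm, but listings and AE reports do not give a comparison of FU values by arm.

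A reader might also infer that FU spirometry and lymphocyte data are dropped altogether. They are not: the EOS and reversibility outputs use them whatever the day. Nor do 6.2 and 11.3.5 contradict each other outright. The spirometry endpoints to EOS can be read as stated exceptions to a default; the tension is confined to the by-visit spirometry summary, which 11.3.5.3 limits to treatment-emergent values.

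**Conclusion.** The point holds in a limited form. As written, FU values from days 31–37 for non-lymphocyte laboratory tests, BP and ECG (by-visit summaries and morphology), and FU spirometry in the by-visit summary and the above-20% count, appear in listings only. Any FU row would describe just the subjects seen on day 30. The conclusion rests on reading the default in 11.3.5 literally and on no SAP exception, which cannot be checked here.

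The size is 7 of 8 permitted calendar days. It is tempting to read this as 88% of FU data lost; the documents do not support that, because nothing is said about when visits actually fall. Nor does it follow that FU abnormalities in most subjects vanish from the abnormality tables. A subject already abnormal within the window is counted, and only an abnormality first seen on days 31–37 is missed. No efficacy result, sample size or error rate is affected. The matter is one of safety reporting and worth correcting because the correction is nearly free.

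**What to change.** In sections 6.2 and 11.3.5, state that scheduled FU-visit laboratory, BP, ECG and spirometry measurements, up to day 37 after the last dose, are summarised for all subjects in a separate FU/post-treatment column or row, including abnormalities seen at that visit. Keep the 30-day limit for AE onset and for treatment-emergent abnormality counts, so that off-drug values are not mixed into on-treatment counts.

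This takes a sentence or so of text and needs no new visits, procedures or data. The downside is one additional displayed column of off-drug values.

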The best (largest) FEV₁, FVC and PEF values from the three acceptable and repeatable tests will be recorded in the eCRF as absolute volume in liters and as flow in liters/second (rounded to two decimal places). These values may come from separate maneuvers. The FEV₁/FVC ratio will be derived from the FVC and FEV₁ values recorded in the eCRF.

Spirometry tests will be conducted according to the ATS/ERS guidelines [[Miller 2005a](#), [Miller 2005b](#)]. The spirometer must fulfill the technical requirements and recommendations for range and accuracy for forced expiratory maneuvers from the ATS/ERS guidelines [[Miller 2005b](#)]. The pulmonary function testing laboratory will ensure that the spirometer is functioning properly and is calibrated according to manufacturer instruction and ATS/ERS guidelines. A copy of the calibrations from the day of test must be stored as source documents in the subject charts at each subject visit, and a log of calibration results must be maintained at the site.

Spirometry testing will be performed by a PFT technician, respiratory therapist or expert, or an equally experienced person according to the ATS/ERS guidelines (e.g., for the US, a registered pulmonary function technologist and/or a registered respiratory therapist). To the extent logically feasible, attempts should be made to have the same tester throughout the study for a subject. For each test, the name of the tester must be stored as source documents in the patient charts. Back-up testers (PFT technician, respiratory therapist, or expert or an equally experienced person according to the ATS/ERS guidelines may conduct spirometry if the primary tester is not available). All PFT technicians or other experienced persons participating in the study will be trained on the specific requirements for the study and be reminded of ATS/ERS recommendations before study start and when compliance issues are identified. In addition, a specific PFT manual will describe the procedures to be implemented by the pulmonary function facility at each investigational site, in order to maintain high quality standards and in order to ensure the validity of the data collected.

Clinically relevant findings meeting the definition of an AE (new AE, or worsening of previously existing condition; see Section [10.1](#)) must be recorded on the AE page of the eCRF.

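### The Protocol defines pulmonary reversibility with *or* in Section 6.2 and the synopsis but with *and* in Section 11.3.5.3; under *or*, a subject past exactly one threshold counts as reversed without any recovery

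*Protocol*

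**What the plan says.** Three places in the Protocol define this endpoint.

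- **Section 6.2 (Safety endpoints).** Entry: "Among subjects with a decrease of > 200 mL or > 12% in" FEV₁ or FVC from baseline to end of treatment (EOT). Outcome: "reversibility defined as a decrease of < 200 mL or < 12" per cent in FEV₁ or FVC, from baseline to the last available follow-up after EOT.
- **Synopsis, safety endpoints.** The same entry and the same *or* outcome.
- **Section 11.3.5.3 (Pulmonary safety).** Entry is unchanged: "For the subset of subjects with a decrease of > 200 mL or > 12% in" FEV₁ or FVC at EOT. The outcome is the number and percentage of subjects "with a decrease of ≤ 200 mL and ≤ 12% from baseline to last available FU", by treatment.

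Entry is therefore the same everywhere. The outcome differs in its connective (*or* against *and*) and in its boundary (< against ≤).

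**The concern.** A reversal criterion should be the opposite of the criterion that put the subject into the subset. The opposite of exceeding either threshold is exceeding neither, so the outcome needs *and*. With *or*, the entry and outcome conditions can be met by the same measurement, and a decline that has not moved can be reported as recovered.

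Pulmonary function is one of the ponesimod risks listed in Section 1.5. Section 1.3.2.4 reports FEV₁ below 80% of baseline at least once in 13.5% of subjects on 20 mg against 3.3% on placebo in Phase 2, and says the FEV₁ decreases were reversible after discontinuation. This endpoint looks at reversibility in the combination with DMF, so its definition should not be able to return a reversal where none occurred. Because the Protocol states both rules, any analysis plan must depart from one section whichever rule it follows.

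**Working it through.** The Protocol states no expected figure for this endpoint, so there is none to reproduce. The check is of the logic first, then of size under stated assumptions.

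**Inputs from the Protocol.** With *d* the fall from baseline and *b* the baseline volume:
- Entry (6.2, synopsis, 11.3.5.3): *d* > 200 mL or *d*/*b* > 12%.
- Outcome in 6.2 and the synopsis: *d* < 200 mL or *d*/*b* < 12%.
- Outcome in 11.3.5.3: *d* ≤ 200 mL and *d*/*b* ≤ 12%.

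**Where the thresholds meet.** 200 mL / 0.12 = 1,667 mL. At any other baseline the two thresholds differ, and a fall lying between them meets one but not the other.

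**Unchanged falls** (fall at follow-up equal to fall at EOT), in 1 mL steps, one measure at a time. The baselines are illustrative.

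| Baseline | 12% of baseline | Unchanged falls counted as reversed, 6.2 | Same, 11.3.5.3 |
|---|---|---|---|
| 1.5 L | 180 mL | 181–199 mL | none |
| 2.0 L | 240 mL | 201–239 mL | none |
| 3.0 L | 360 mL | 201–359 mL | none |
| 3.5 L | 420 mL | 201–419 mL | none |
| 4.0 L | 480 mL | 201–479 mL | none |
| 5.0 L | 600 mL | 201–599 mL | none |

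**Single subjects.**
- Baseline 3.5 L, fall 300 mL, unchanged: 300/3,500 = 8.6%. Enters on > 200 mL; reversed under 6.2 (8.6% < 12%); not reversed under 11.3.5.3.
- Baseline 3.0 L, fall grows from 210 to 350 mL: 350/3,000 = 11.7%. Reversed under 6.2 although worse; not reversed under 11.3.5.3.
- Baseline 3.0 L, fall 400 mL, unchanged: 400/3,000 = 13.3%. Past both thresholds; not reversed under either rule.
- Baseline 3.0 L, fall 400 mL easing to 150 mL (5.0%): reversed under both rules.

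**Size, on assumed inputs.** The Protocol gives no distribution of baselines or falls. The assumptions, all mine: baseline FEV₁ normal with SD 0.7 L; fall at EOT normal with SD 0.25 L; means as below. Simulation gives the percentage of the subset called reversed.

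| Recovery | Baseline mean | Mean fall | *or* rule | *and* rule |
|---|---|---|---|---|
| None | 2.8 to 3.6 L | 0.2 to 0.3 L | 33–62% | 0% |
| None | 3.2 L | 0.2 L | 52% | 0% |
| None | 3.2 L | 0.3 L | 43% | 0% |
| Half of the fall | 3.2 L | 0.2 to 0.3 L | 91–94% | 47–58% |
| 80% of the fall | 3.2 L | 0.2 to 0.3 L | about 100% | about 100% |

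With no recovery and a 3.2 L baseline, mean falls of 0 and 0.1 L give 66% and 59% under *or*. The mislabelled percentage therefore goes down as falls get larger.

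**The case against.** The section that describes the analysis, 11.3.5.3, already has the right rule. The inflated figure appears only if the programming follows the endpoint list instead. The endpoint is descriptive, with no hypothesis or power attached. Recovery is also shown without any threshold: change to end of study against change to EOT is a separate endpoint in 6.2, and 11.3.5.3 plans mean plots with confidence intervals and a subject-level scatter plot, where a persistent 300 mL loss would be visible. All of this stands, and it limits the severity.

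It does not remove the contradiction. All three statements are current Protocol text and give different answers for the same subject.

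A reader might infer three stronger things that the document does not support:

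- **That every subject without recovery is called reversed.** An unchanged subject past both thresholds is not reversed under either rule.
- **That the error favours ponesimod.** If more subjects decline on ponesimod, more of them by count could be mislabelled. But 11.3.5.3 also reports a percentage within the subset, and in the model above that percentage is inflated more where falls are smaller. No direction by arm can be claimed for it.
- **That the last available follow-up is itself an error.** Sections 6.2 and 11.3.5.3 agree on it. For treatment completers the end-of-study visit is Visit 20 (Section 3.5.3.3), so a long delay concerns those who enter the post-treatment observation period. Visit 20 can also be combined with EOT after an interruption of more than 30 days (Sections 8.2.10 and 8.3.1.2), so it does not give everyone a separate later reading.

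**Conclusion.** The reversibility rule in Section 6.2 and the synopsis is wrong as written and contradicts Section 11.3.5.3. The logical result needs no assumption: at any baseline other than 1.67 L there is a band of unchanged falls that the *or* rule calls reversed and the *and* rule does not. The number reversed is overstated wherever such falls persist.

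How many subjects this would touch cannot be known from the Protocol. The 33–62% is a worst case that rests on assumed distributions and on no recovery at all; Section 1.3.2.4 gives reason to expect substantial recovery, and at 80% recovery the two rules nearly agree.

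A smaller looseness is shared by all three places: naming FEV₁ or FVC in both the entry and the outcome lets a subject, on a literal reading, enter on one measure and reverse on the other.

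This should be fixed, but it is not critical: the endpoint is a descriptive safety summary, and the primary analysis, alpha and sample size are unaffected.

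**What to change.** In Section 6.2 and the synopsis, define reversibility as a decrease from baseline of at most 200 mL and at most 12%, matching Section 11.3.5.3 in connective and boundary. In all three places, add that entry and reversal are judged on the same measure, with FEV₁ and FVC summarised separately.

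A supportive summary restricted to Visit 20, where spirometry is already scheduled, is optional.

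The cost is a few words in Section 6.2 and the synopsis and one clarifying sentence in each of the three places, with no new assessment. The reported reversibility percentage can be lower than under the *or* rule, but not higher. The change should be made before unblinding.
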